3.0 Investigational Plan / Schema

This is a single site Phase 2 interventional pilot study of euthyroid hypothyroxinemia in patients diagnosed with metastatic breast carcinoma. The study will enroll approximately 30 participants. It is anticipated that recruitment will take up to four (4) years. End of the study is the date of the last visit or last scheduled procedure for the last patient. An Intent-to Treat (ITT) population with a priori planned subgroup analysis will be used for analysis purposes.

Study Design: All enrolled participants will undergo baseline screening lab work (TSH, FreeT3, FreeT4, CBC, CMP), EKG and physical examination. Once it is determined that they meet eligibility criteria they will have their L-thyroxine (T4) discontinued and Triiodothyronine (T3) initiated. The Triiodothyronine (T3) will be titrated by the investigator to

maintain levels of free T4 < 50% normal range. Treatment duration will be 9 months. Disease status will be assessed at 3, 6, 9, and 12 months.

Eligibility Criteria

- Age greater than or equal to 18
- Male or female with diagnosis of metastatic breast carcinoma and documented history of hypothyroidism .
- TSH level within normal range at baseline
- Life expectancy estimated > 3 months
- Ability and willingness to provide informed consent

Exclusion Criteria

- Life expectancy estimated to be less than 3 months
- Is currently pregnant or intends to become pregnant during the duration of the study
- Active angina, NYHA advanced [Class III/IV] CHF, or uncontrolled cardiac arrhythmia within 6 months of enrollment
- History of thyrotoxicosis or adrenal insufficiency unless previously treated > 5 years ago and resolved without active replacement hormonal therapy as per Principal Investigator discretion.
- Hypersensitivity to any active or extraneous constituents in Cytomel/liothyronine sodium

4.0 Study Procedures

It is anticipated that 20% of the patients with metastatic breast cancer will qualify for participation in this study. Patients who screen fail after meeting initial eligibility will be asked to allow record follow-up so the data can be used for the initial endpoint of prevalence. Rescreening will not be permitted.

Following consent and confirmation of eligibility participants will have their L-thyroxine (T4) discontinued and Triiodothyronine (T3)/liothyronine sodium initiated at 3: 1 mcg respectively. Study will allow use of Triiodothyronine (cytomel/liothyronine) and all available generic liothyronine sodium compounds. Triiodothyronine dosing will be rounded up to the closest commercial dose available. For patients on L-thyroxine there will be a washout period of four (4) days between discontinuation and the initiation of triiodothyroinine. Day 0 will be the day of enrollment. Day 1, or day 5 (if washout required) will be the day of the first dose of Triiodothyronine treatment. Triiodothyronine tablets are administered orally as a once a day dosing, or split dosing at the Investigators discretion. Usual maintenance dose is 25 to 75mcg daily. It will be recommended that the drug be taken at the same time each day, but this is not mandatory.

Drug titration will be in accordance with thyroid function testing to maintain levels of free T4 at <50% normal range. The treatment period will continue for 9 months (270 days). In the event of loco/regional recurrence or progression there is no need to discontinue study treatment because this is not one of the endpoints.

During the treatment period participants will have lab testing every 4 weeks for the first 12 weeks and then every 12 weeks until study drug is discontinued. Participants will be scheduled for a clinic visit every 12 weeks. Compliance with Triiodothyronine (T3) and adverse events will be assessed at each clinic visit. Disease state will be assessed at 3, 6, 9, and 12 months via clinical examination, laboratory results and radiographic findings performed as part of routine care. Participants will also be asked to complete a Quality of Life survey (FACT-B) at each clinic visit.

Unscheduled visits and management for metastatic breast cancer are at the discretion of the investigator. Unscheduled visits may include physical examinations, vital signs, ECOG performance status, concomitant medication, adverse event collection, disease symptoms assessment, laboratory testing, Triiodothyronine (T3) dose adjustments, or to resumed dosing, if previously interrupted.

Discontinuation of Study Treatment: At the end of the treatment period, the investigator will have the discretion to resume thyroxine or continue Triiodothyronine (T3); however, if it is not covered by insurance the patient will be responsible.

If subjects discontinue study treatment prematurely for any reason they will be asked to continue follow-up until study completion.

All patients will be scheduled for a 12-month safety follow-up visit.

TABLE 1: SCHEDULE OF STUDY PROCEDURES

Study Phase	Screening	Study Visits			Follow Up Visit
Visit		3mo (+/- 14 days)	6mo (+/- 14 days)	9mo (+/- 14 days)	12mo (+/- 14 days)
ECOG PS	X	X	X	X	X
Informed Consent	X				
Review Inclusion/Exclusion Criteria	X				
Demographics/Medical History	X				
Physical Examination	X	X	X	X	X
Vital Signs: BP, HR, RR	X	X	X	X	X
EKG	X				
Disease assessment	X	X	X	X	X
FACT-B QOL questionnaire	X	X	X	X	X
Prior/Concomitant Medications	X	X	X	X	X
Clinical Laboratory Evaluation*	X	X	X	X	X
Pregnancy Test (women of childbearing potential only)	X				
Adverse Event Assessment	X	X	X	X	X

- *TSH, FreeT3, FreeT4, CBC, CMP every 4 weeks for the first 12 weeks and then every 12 weeks until end of study.
- Additional lab work at physician's discretion.

Study Drug

Cytomel (liothyronine sodium) is a commercially available compound which is a synthetic formulation of triiodothyronine. Study drug may be obtained from the Aultman Hospital Retail Pharmacy or the pharmacy of the participant's choice. The cost will be charged to the participant/insurance company unless they meet the hospital's indigent policy, in which case study drug will be provided free of charge.

Cytomel capsules should not be opened, crushed, or chewed. Patients should store the Cytomel capsules in the original package provided and be instructed to keep all medication out of reach of children. Further details obtained from accessdata.fda.gov can be found in appendix D.

HOW SUPPLIED

Cytomel (liothyronine sodium) Tablets: 5 mcg in bottles of 100;

25 mcg in bottles of 100; and 50 mcg in bottles of 100.

5 mcg 100's: NDC 52604-3414-1

25 mcg 100's: NDC 52604-3416-1

50 mcg 100's: NDC 52604-3417-1

Store between 15° and 30°C (59° and 86°F).

The Investigator is submitting this study as IND exempt. Cytomel or liothyronine sodium are being used in this study in accordance with approved indications.

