Precautions: Thyroid hormones should be used with great caution in a number of circumstances where the integrity of the cardiovascular system, particularly the coronary arteries, is suspected. These include patients with angina pectoris or the elderly, in whom there is a greater likelihood of occult cardiac disease. In these patients, liothyronine sodium therapy should be initiated with low doses, with due consideration for its relatively rapid onset of action.

Thyroid hormone therapy in patients with concomitant diabetes mellitus or insipidus or adrenal cortical insufficiency aggravates the intensity of their symptoms. Appropriate adjustments of the various therapeutic measures directed at these concomitant endocrine diseases are required. Hypothyroidism decreases, and hyperthyroidism increases the sensitivity to oral anticoagulants. Prothrombin time should be closely monitored in thyroid-treated patients on oral anticoagulants and dosage of the latter agents adjusted on the basis of frequent prothrombin time determinations.

In cases of concomitant diabetes mellitus, the daily dosage of antidiabetic medication may need readjustment as thyroid hormone replacement is achieved. If thyroid medication is stopped, a downward readjustment of the dosage of insulin or oral hypoglycemic agent may be necessary to avoid hypoglycemia. At all times, close monitoring of urinary glucose levels is mandatory in such patients.

Potential Benefits of Study Participation

Direct benefits are unknown, but intervention may improve quality of life and prolong progression free survival.

Indirect benefits for the greater good of society and science.

Recruitment Strategy

Patients with the diagnosis of metastatic breast cancer and estimated life expectancy of greater than 3 months will be identified either by the investigators from within their practice or referred by other oncologists in the community.

Potential and eligible participants will be screened by collection of data (via medical record review, direct query or other procedures), and this screening will take place before subjects' consent to participation in the study.

Investigator will notify and coordinate care with all physicians involved in the patients care, specifically primary care physician (PCP), endocrinologist and cardiologist.

Informed Consent/Assent and HIPAA Authorization

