6.0 Safety Management

Data Monitoring

The investigator will ask the HRRB/Compliance Office to assign a data monitor to review each case for eligibility, adherence to the protocol, occurrence of adverse events, and accuracy of data. The first review will be conducted after enrolling the first 5 patients. Regular reviews will be scheduled at increments of 10 randomized patients until enrollment goals are met. Unscheduled random chart audits may be performed to ensure data integrity. Any deficiencies found during these reviews will be addressed and reported to the PI, HRRB and federal agencies as appropriate.

Clinical Adverse Events

Clinical adverse events (AEs) will be monitored throughout the study by the Principal Investigator.

Definition of an Adverse Event

An adverse event is any untoward medical occurrence in a subject who has received an intervention (drug, biologic, or other intervention). The occurrence does not necessarily have to have a causal relationship with the treatment. An AE can therefore be any unfavorable or unintended sign (including an abnormal laboratory finding, for example), symptom, or disease temporally associated with the use of a medicinal product, whether or not considered related to the medicinal product.

All AEs (including serious AEs) will be noted in the study records with a full description including the nature, date and time of onset, determination of non-serious versus serious, intensity (mild, moderate, severe), duration, causality, and outcome of the event.

Definition of a Serious Adverse Event (SAE)

An SAE is any adverse drug experience occurring at any dose that results in any of the following outcomes:

- death,
- a life-threatening event (at risk of death at the time of the event),
- requires inpatient hospitalization or prolongation of existing hospitalization,
- a persistent or significant disability/incapacity, or

- a congenital anomaly/birth defect in the offspring of a subject.

Important medical events that may not result in death, be life-threatening, or require hospitalization may be considered a serious adverse drug event when, based upon appropriate medical judgment, they may jeopardize the subject and may require medical or surgical intervention to prevent one of the outcomes listed in this definition.

Relationship of SAE to study drug or other intervention

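### Section 4.0 starts every switched participant on liothyronine at 3:1, rounded up, while the 5.0 Precautions call for a low-dose start in the elderly; the protocol does not say which governs

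*Protocol*

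**What the plan says.** **The dosing rule.** Section 4.0 (Study Procedures) says that "participants will have their L-thyroxine (T4) discontinued and Triiodothyronine (T3)/liothyronine sodium initiated at 3: 1 mcg respectively". It then directs that the dose be rounded up to a commercially available one. A four-day washout separates the two drugs. The only discretion that 4.0 gives over the first dose is whether to take it once daily or split. Later titration follows thyroid function tests, with free T4 as the target. Section 4.0 does not refer to the Precautions.

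**The precaution.** Section 5.0 (Risk Assessment, Precautions) describes patients in whom the integrity of the cardiovascular system is in doubt: "These include patients with angina pectoris or the elderly, in whom there is a greater likelihood of occult cardiac disease". It continues: "In these patients, liothyronine sodium therapy should be initiated with low doses, with due consideration for its relatively rapid onset of action". It states no dose in mcg and no age.

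**Who can enrol.** Section 3.0 sets "Age greater than or equal to 18" with no upper limit. The cardiac exclusion is "Active angina, NYHA advanced [Class III/IV] CHF, or uncontrolled cardiac arrhythmia within 6 months of enrollment". Participants must also have "TSH level within normal range at baseline".

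**The concern.** Both instructions concern initiation, so later titration cannot reconcile them. An investigator with an elderly participant who follows 4.0 gives the full converted dose, rounded up, and may depart from the Precautions. One who starts low departs from 4.0 as written. Section 6.0 has a data monitor review each case for adherence to the protocol, and the monitor could not tell from the text which of the two complied.

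What is at stake is the safety of the first weeks of treatment in a small subgroup. The Precautions base their caution on occult cardiac disease and rapid onset of action, and the Risk Assessment says that overdose may induce or aggravate angina or congestive heart failure. Estimation of progression-free survival is not at issue.

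**Working it through.** No statistical figure in the protocol needs reproducing. The check compares the texts and then illustrates the dosing rule.

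**Step 1: do both rules reach the same participants?**
- Elderly: yes. Section 3.0 has no upper age limit, 4.0 has no age exception, and the Precautions name the elderly. No inference is needed.
- Angina: only in part. Active angina is excluded, so the angina patients who can still enrol are those with a past or inactive history. That category is an inference; the protocol does not name it.
- Participants not taking L-thyroxine have no prior dose to convert, so the point concerns those who are switched.

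**Step 2: what first dose does 4.0 produce?**

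Inputs: the 3:1 conversion and upward rounding (4.0); tablet strengths of 5, 25 and 50 mcg (Study Drug, How Supplied). Doses are assumed to be made up in 5 mcg multiples. The protocol gives no distribution of L-thyroxine (T4) doses, so the doses below are assumptions.

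First dose = 5 × ceil(T4 / 15).

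| Assumed T4 (mcg) | T4 / 3 | First dose under 4.0 (mcg) | Increase from rounding |
|---|---|---|---|
| 50 | 16.7 | 20 | 20% |
| 75 | 25.0 | 25 | 0% |
| 100 | 33.3 | 35 | 5% |
| 150 | 50.0 | 50 | 0% |

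Thresholds: the first dose reaches 25 mcg when T4 exceeds 60 (ceil(T4/15) is then at least 5). It reaches 50 mcg when T4 exceeds 135 (at least 10). If the rounding sentence meant a single tablet of 5, 25 or 50 mcg, the thresholds would fall to 15 and 75 mcg (T4/3 above 5 and above 25). Nothing below relies on that reading.

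**Step 3: can the excess over a low dose be calculated?** No. The Precautions give no mcg value, and the package insert listed in 10.0 is not reproduced. What can be said is that rounding never lowers the dose, and that 4.0 offers no route to a lower start.

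**Step 4: do other provisions settle the first dose?**
- Before dosing: a screening EKG and physical examination, and "Investigator will notify and coordinate care with all physicians involved in the patients care, specifically primary care physician (PCP), endocrinologist and cardiologist". Neither says which rule prevails.
- After dosing: "Clinical adverse events (AEs) will be monitored throughout the study by the Principal Investigator"; unscheduled visits with dose adjustment are allowed; further laboratory tests are at the physician's discretion; and the dose is reduced or interrupted if signs of overdose appear. All of these follow exposure. The first scheduled tests come at 4 weeks, clinic visits are every 12 weeks, and EKG is scheduled only at screening.

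**The case against.** The strongest reply is that the exception already exists. A specific precaution for a subgroup ordinarily qualifies a general dosing rule, so on a fair reading the Precautions modify 4.0 and only a cross-reference is missing. That reading is available, but the protocol does not adopt it. Section 4.0 is the operative dosing text and gives a number; 5.0 is risk text and gives none. The reply lowers the severity without removing the ambiguity.

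The package insert might also quantify a low start. That cannot be checked here, and a number in an appendix would still not say which section governs.

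A reader might infer three stronger claims that the documents do not support:

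- *That the 3:1 dose is shown to be too high.* Without a mcg value for a low dose, it cannot be shown that 20 mcg, for example, exceeds it.
- *That a first dose inside the protocol's usual maintenance range of 25 to 75 mcg is itself a fault.* Switched participants are already on replacement, enter with a normal TSH and receive a dose scaled to what they took. Landing in the maintenance range is what such a switch would be expected to do.
- *That patients with angina are generally exposed.* Active angina is excluded, and the remaining group is inferred.

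The safeguards in Step 4 also stand. They lower the risk, but they do not resolve which instruction applies on the first day of dosing.

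**Conclusion.** The point holds as an inconsistency between two sections on the first liothyronine dose. It rests on explicit text for elderly participants and on inference for those with a history of angina that is not active. Severity is minor, and the change is a cheap improvement.

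Its size is not calculable. The documents give no mcg value for a low dose, no definition of elderly, and no age or L-thyroxine dose distribution for the approximately 30 participants. The doses in the table illustrate the rule under assumed L-thyroxine doses and 5 mcg steps; they do not measure harm.

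**What to change.** Insert in 4.0, directly after the rounding sentence:

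*For elderly participants (age stated by the sponsor) and those with suspected coronary disease or past angina, the low-dose start in 5.0 Precautions governs instead of the 3:1 conversion. Do not round up. Start below the 3:1 dose using 5 mcg tablets, at a level set by the investigator with the cardiologist or endocrinologist, and step up toward the 3:1 dose by symptoms and thyroid tests.*

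Leave 4.0 unchanged for everyone else.

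**What it guarantees.** The highest start allowed is the largest multiple of 5 strictly below T4/3. For 50, 75, 100 and 150 mcg of L-thyroxine this is 15, 20, 30 and 45 mcg, against 20, 25, 35 and 50 now. The guaranteed cut is therefore only one 5 mcg step in each example. The main gain is that precedence is stated, and any lower start becomes a documented clinical decision. A fixed limit below 25 mcg would cut further, but it would hold a participant on 150 mcg to at most 20 mcg, which is 20/50 = 40% of the 3:1 dose. That risks under-replacement, with the first scheduled tests only at week 4.

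**Cost.** A short insertion and one age for the sponsor to state. It needs no new scheduled visits or tests, and the 5 mcg tablet is already listed. The downside is temporarily lower replacement and possibly a longer time to euthyroid hypothyroxinemia, a secondary endpoint, in this subgroup.

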2.0 Primary Objective

1. To prospectively evaluate the progression-free survival in hypothyroid patients with metastatic breast carcinoma who are rendered euthyroid and hypothyroxinemic.

Secondary Objectives

1. To quantitate the prevalence of hypothyroidism in metastatic breast cancer patients.
2. To monitor QOL at baseline, 3, 6, 9 and 12 months.
3. To prospectively study the feasibility and average time required to achieve the euthyroid hypothyroxinemia state in qualifying patients.

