7.0 Statistical Methods

Baseline Data

Baseline and demographic characteristics will be summarized by standard descriptive summaries (e.g., means and standard deviations for continuous variables such as age and percentages for categorical variables such as gender).

Analysis of Primary Outcome of Interest

The primary analysis will include all subjects meeting all inclusion and exclusion criteria and completing Visit 1.

The primary endpoint will be the progression free survival at 12 months

Secondary endpoints will include:

- the prevalence of hypothyroidism in successive metastatic breast cancer patients,
- the change in QOL measures between baseline, 3, 6, 9 and 12 months and
- the duration of time to achieve the euthyroid hypothyroxiemic state

Sample Size and Power

The sample size is estimated to be approximately 30 patients.

Given the many uncertainties to calculate power precisely, this is an estimate made, based on clinical experience.

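### Section 4.0 says loco/regional recurrence or progression is not an endpoint, although progression-free survival is the primary endpoint

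*Protocol*

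**What the plan says.** The sentence is in Protocol section 4.0 (Study Procedures), in the paragraph on titration and the 9-month treatment period: "In the event of loco/regional recurrence or progression there is no need to discontinue study treatment because this is not one of the endpoints".

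Three other places bear on it:

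- Section 2.0, the only primary objective: "To prospectively evaluate the progression-free survival in hypothyroid patients with metastatic breast carcinoma who are rendered euthyroid and hypothyroxinemic".
- Section 7.0: "The primary endpoint will be the progression free survival at 12 months".
- Section 3.0: "Disease status will be assessed at 3, 6, 9, and 12 months". Section 4.0 repeats the schedule and names the sources: "Disease state will be assessed at 3, 6, 9, and 12 months via clinical examination, laboratory results and radiographic findings", obtained in routine care. Table 1 lists a disease assessment at screening and at each of the four visits. None of these makes an exception for loco/regional disease.

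Section 4.0 also provides that patients who stop study treatment early are asked to remain in follow-up until study completion.

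**The concern.** Progression is a component of PFS. A protocol cannot have PFS as its primary endpoint and also tell its staff that a form of progression is not an endpoint, unless it defines PFS to leave that form out. This protocol does not.

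What is at stake is event classification. The protocol names no progression criteria, so the section 4.0 sentence is the only text that tells staff how a particular kind of progression relates to the endpoints, and it points away from counting it. If staff or the analyst followed it, a loco/regional progression found at a scheduled assessment would not be an event, and the patient would stay progression-free until some later counted event. With follow-up to month 12, leaving out events cannot lower 12-month PFS and can raise it. In a single-arm study there is no comparison group in which the same error could cancel out.

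**Working it through.** **Text comparison.** The protocol states no figure on this point, so the finding rests on the wording.

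1. Sections 2.0 and 7.0 use PFS without qualification, and no other section limits it to distant progression.
2. The section 4.0 phrase can be read in two ways. If loco/regional qualifies both nouns, one kind of progression is declared not to be an endpoint. If it qualifies recurrence only, progression of every kind is so declared, and the conflict is wider. Both readings contradict sections 2.0 and 7.0.
3. A third reading takes the pronoun to refer to stopping treatment. It fits poorly, because the sentence opens with the event of recurrence or progression, and it would still leave the status of that event unclear.
4. The rule to continue treatment does not conflict with PFS. Assessments and follow-up go on regardless, so the events can still be observed. Only the stated reason is wrong.

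**Size, as an illustration.** Only n of about 30 comes from the protocol (sections 3.0 and 7.0). Assumed: true 12-month PFS S = 0.40; loco/regional share of PFS events f = 0.10, 0.20 or 0.30; none of these counted; constant hazards with total L = −ln S per 12 months. This uses the narrower reading in step 2.

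Apparent PFS is S plus the probability of an uncounted progression at time t followed by no counted event up to month 12.

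*Case 1: the counted-event hazard stays at (1−f)L afterwards.* The sum reduces to S^(1−f).

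*Case 2: the hazard rises to 2L afterwards.* The sum reduces to S + f·S·(1−S).

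| f | Case 1 | Gain (points) | Case 2 | Gain (points) |
|---|---|---|---|---|
| 0.10 | 0.40^0.9 = 43.8% | +3.8 | 0.40 + 0.10×0.24 = 42.4% | +2.4 |
| 0.20 | 0.40^0.8 = 48.0% | +8.0 | 0.40 + 0.20×0.24 = 44.8% | +4.8 |
| 0.30 | 0.40^0.7 = 52.7% | +12.7 | 0.40 + 0.30×0.24 = 47.2% | +7.2 |

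In patients, case 1 runs from 30×0.038 = 1.1 to 30×0.127 = 3.8, and case 2 from 30×0.024 = 0.7 to 30×0.072 = 2.2. With S varied from 0.30 to 0.60 and f from 0.10 to 0.30, the gain is +3.1 to +13.1 points in case 1 and +2.1 to +7.5 in case 2.

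**Cross-check without a hazard model.** If all 30 patients are followed to month 12, each loco/regional progression left out in a patient with no other PFS event adds 1/30 = 3.3 points. With 15 true events, PFS is 15/30 = 50.0% (exact 95% interval 31.3 to 68.7). Leaving out three such events gives 18/30 = 60.0% (40.6 to 77.3).

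**For scale.** The approximate 95% half-width at S = 0.40 and n = 30 is 1.96×√(0.40×0.60/30) = 17.5 points.

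**The case against.** The strongest reply is that the sentence is a treatment rule and not an event definition. It answers whether study drug must stop, section 7.0 does not refer to it, and disease assessment continues without exception. Harm needs a further step that the protocol does not take. This is right as to consequence, which is why the inflation is put as conditional. It does not make the stated reason true.

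A statistical analysis plan may exist and define a PFS event. That is fair, and the absence of a definition is not the complaint here. But a definition that counted loco/regional progression would leave the section 4.0 sentence in conflict with it, and one that did not would narrow the endpoint that sections 2.0 and 7.0 state without limit.

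The sponsor might have meant to exclude these events, in which case the difference is one of definition and not of bias. Nothing in the protocol supports a distant-only PFS. Counting any progression is the plain meaning of the endpoint as written.

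Finally, the illustrated sizes rest almost wholly on assumptions, they are below the sampling half-width, and section 7.0 gives no reference rate or success threshold that they could tip. All of this stands and limits the weight of the point. Even so, wider sampling error does not excuse a systematic error in the favourable direction.

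**Conclusion.** The concern holds. The reason given in section 4.0 contradicts the primary objective in section 2.0 and the primary endpoint in section 7.0, on either reading of loco/regional. Confidence in that contradiction is high, because it is on the face of the text.

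Whether any event would be misclassified cannot be known from the protocol. If all loco/regional progressions went uncounted, the assumed inputs put the inflation of 12-month PFS at 2.4 to 12.7 points for a true value of 40%. The upper part of that range needs a 30% loco/regional share and no rise in hazard after the uncounted progression. The point should be fixed because it touches the primary endpoint and the remedy is slight.

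**What to change.** In section 4.0, delete the clause that gives endpoint status as the reason. Add that progression, including loco/regional progression, counts as a PFS event at its first documented date whether or not study treatment continues, so that sections 2.0, 4.0 and 7.0 agree. Whether treatment continues after such an event is a separate clinical matter, and no change to it is proposed.

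The cost is one sentence in an amendment. Reported PFS may be lower than it would be if these events were left out.

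### Do 12-weekly clinic visits miss the 9- and 12-month windows and distort 12-month progression-free survival?

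*Protocol*

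**What the plan says.** Protocol section 4.0 (Study Procedures) describes the visit schedule twice. In the text, one paragraph begins "During the treatment period participants will have lab testing every 4 weeks for the first 12 weeks and then every 12 weeks until study drug" ends, and continues "Participants will be scheduled for a clinic visit every 12 weeks". Compliance, adverse events and the FACT-B questionnaire are attached to those clinic visits. The same paragraph then says "Disease state will be assessed at 3, 6, 9, and 12 months". Table 1 gives columns for 3, 6, 9 and 12 months, each with a tolerance of 14 days either way, and marks both disease assessment and FACT-B in all four. Section 3.0 also lists disease assessment at those four months.

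Treatment lasts 9 months, which section 4.0 equates with 270 days. After treatment, "All patients will be scheduled for a 12-month safety follow-up visit"; Table 1 gives this visit its own follow-up column. On the time origin, "Day 0 will be the day of enrollment", and the first dose is on day 1, or on day 5 where a washout is needed.

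Section 7.0 (Statistical Methods) says "The primary endpoint will be the progression free survival at 12 months". It names no estimator, no day on which a curve is read and no rule for dating progression.

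**The concern.** Twelve weeks is 84 days and three months is about 90, so a 12-week cadence drifts earlier by about 6 days per visit. By the third visit the drift exceeds the 14-day tolerance. If the cadence ran on to a fourth visit, the last assessment would come before the 12-month window opens, and a patient last seen then would not be known to be progression-free at 12 months.

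A second worry comes from the tolerance itself. A 12-month visit may fall up to 14 days after the landmark. If progression is dated at the visit that finds it and a curve is read at exactly 12 months, a patient found to have progressed at a late visit counts as progression-free. The primary result would then depend partly on appointment dates. In a trial of about 30 patients, one or two reclassified patients would be visible.

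**Working it through.** **Inputs.** Visit interval 12 × 7 = 84 days (section 4.0 text); targets at 3, 6, 9 and 12 months with a tolerance of 14 days (Table 1); 9 months = 270 days (section 4.0).

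**Conversion.** 270 / 9 = 30 days per month, so the stated figure is reproduced exactly with 30-day months. Calendar months (30.4375 days) are shown as a second reading.

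**Windows against 12-week visits.** Visit *k* falls on day 84*k*; the window is (3*k* × month length) ± 14.

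| Target | Visit day | Window, 30-day months | Result | Window, calendar months | Result |
|---|---|---|---|---|---|
| 3 months | 84 | 76–104 | inside | 77.3–105.3 | inside |
| 6 months | 168 | 166–194 | inside | 168.6–196.6 | 0.6 day early |
| 9 months | 252 | 256–284 | 4 days early | 259.9–287.9 | 7.9 days early |

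**Time origin.** Counting visits from a first dose on day 1 and months from day 0 puts the third visit on day 253, 3 days early with 30-day months. Counting from a day-5 first dose puts it on day 257, inside by 1 day (2.9 days early with calendar months). The miss is therefore not certain for every patient, though the one variant that fits mixes two origins.

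**Month 12.** A fourth 12-week visit would fall on day 336, which is 346 − 336 = 10 days before the window. The protocol does not contain that visit. The sentence on clinic visits belongs to a paragraph about the treatment period, which ends at 9 months, and the 12-month visit is scheduled in its own right. Only Table 1's laboratory footnote carries a 12-week interval to the end of the study, and it concerns blood tests.

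**Effect of an early third visit on the primary endpoint.** Suppose 12-month status is taken from the 12-month visit. A progression between day 252 and the 9-month window is then found at the 12-month visit rather than the third one, and the patient counts as progressed by 12 months either way. The third visit's date does not alter that status.

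**Effect of the tolerance, if a visit-dated curve were read at 12 months.** This needs assumptions the protocol does not make: exponential progression times with medians of 6 to 24 months, assessments at 3, 6, 9 and 12 months, and progression dated at the visit. Read at day 360, with visit dates uniform over the window:

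- median 6 months: true 25.0%, read 30.3% (+5.3 points)
- median 12 months: true 50.0%, read 54.9% (+4.9 points)
- median 24 months: true 70.7%, read 74.0% (+3.3 points)

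If every visit ran 14 days late, the excess would be 33.5 − 25.0 = 8.5 points at a 6-month median and 76.1 − 70.7 = 5.4 points at 24 months. When status is taken at the 12-month assessment and visits are uniform over the window, the estimate matches the true value (25.0%, 50.0% and 70.7%).

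**Sampling error.** The 95% half-width with 30 patients is 1.96 × √(0.3 × 0.7 / 30) = 16.4 points at 30%, and 1.96 × √(0.5 × 0.5 / 30) = 17.9 points at 50%.

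**The case for a change.** The strongest case for acting is that this is a contradiction within the protocol, not a detail left for later. A site that follows the text to the letter reaches its last on-treatment visit outside the window, and section 6.0 has a monitor review each case for adherence. The correction would cost a word, and one more sentence could tie 12-month status to the 12-month visit, which the calculation shows to be essentially unbiased under even visit spread.

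The first part stands: the two wordings differ and should be reconciled into one calendar. Which one is meant is for the sponsor to say. But the consequence is confined to FACT-B, compliance and adverse-event visits that come 4 days before a window opens. Table 1 itself marks laboratory tests at 3, 6, 9 and 12 months and footnotes them as 12-weekly, so the authors evidently use the two expressions interchangeably.

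The second part does not stand as a fault. The bias belongs to a visit-dated curve read on a fixed day, which section 7.0 does not specify. It also does not arise from the 12-week sentence, since 12-week visits run early and the bias needs late ones. The reading day and dating rule commonly belong to a statistical analysis plan, which was not among the documents examined, and taking status from the 12-month assessment is already a natural reading of sections 4.0 and 7.0.

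**Conclusion.** The schedule mismatch is genuine and small: 4 days at the 9-month visit with the protocol's 30-day months and a common origin, about 8 days with calendar months, and none if visits count from a day-5 dose and 30-day months from day 0. It does not reach the 12-month visit or the stated times of disease assessment. With one arm and no stated hypothesis test, a questionnaire or safety visit a few days early changes no conclusion.

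The effect on 12-month progression-free survival is hypothetical. It appears only under an assumed estimator, and with evenly spread visits it is about 3 to 5 points, well inside the trial's sampling error. The larger figure of about 5 to 9 points requires every visit to be 14 days late. This conclusion rests on analysts taking 12-month status from the 12-month assessment, or on an analysis plan that sets an equivalent rule. The wording is a clerical slip to be reconciled when the protocol is next revised; the design and analysis need no change on this account.
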